**ABBREVIATIONS AND DEFINITIONS OF TERMS**

AE	Adverse Event
Pain Scales	
Include but are not limited to:
 
Face, Legs, Activity, Cry, Consolability (FLACC)  - <math>\geq</math> 7 years of age; may be used in the older child
 
Revised Face, Legs, Activity, Cry, Consolability (rFLACC)  - <math>\geq</math> 7 years of age; may be used in the older child
 
FACES Pain Scale Revised (FPS-R)  - <math>\geq</math> 3 years of age; may be used in the older neurologically impaired, non-verbal child
 
Numeric Pain Scale  - <math>\geq</math> 8 years of age; cognitively intact patients, able to self-report

AMI	Actuated Medical, Inc.
BMI	Body Mass Index
BSA	Body Surface Area
CHOP	The Children's Hospital of Philadelphia
DOB	Date of Birth
EAD	Enteral Access Device
J	Jejunostomy Tube
ND	Nasoduodenal Tube
NG	Nasogastric Tube
NJ	Nasojejunal Tube
AMT GJ	Applied Medical Technology, Inc. Gastrojejunral 14 Fr Tube
EAD(A)	Adult Feeding and Decompression Access Device ND, NG, NJ, G, and J Tubes of size 10 – 18 Fr, 10 – 140 cm
EAD(P)	Pediatric Enteral Access Device ND, NG, and NJ 6 – 8 Fr, 38 – 140 cm; and NG tube (Corflo, Corpak MedSystems) used as a J tube inserted through a G tube 6 – 8 Fr, 38 – 140 cm; GJ tube (AMT) 14 Fr, 38 – 140 cm (15 – 55 in)
EAD(P) Adverse Event	EAD displacement, EAD damage, enteral tract tissue injury

EHR	Electronic Health Record
EPIC	Integrated Electronic Health Record system used at The Children's Hospital of Philadelphia
Fr	French gauge (conventional unit of measure used to describe tube diameter size (1 Fr = 0.33 mm))
IR	Interventional Radiology
MRN	Medical Record Number
MUSC	Medical University of South Carolina
NIH / NICHD	National Institutes of Health / National Institute of Child Health and Human Development
PCU	Progressive Care Unit
PICU	Pediatric Intensive Care Unit
SBIR	Small Business Innovation Research
Tube	Feeding tube
USA	United States of America

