### **Safety Monitoring:**

[figure not shown]
This study will incorporate a data and safety monitoring plan with medical monitor to review study data for adverse events to ensure the safety of study subjects. Following the use of either standard treatment or TubeClear® intervention, all Subjects will receive an abdominal radiograph with contrast. Radiographs will be reviewed by a radiologist (blinded to the study) to assess for tube integrity and location, and enteral tract tissue injury that may be attributable to either intervention.

In all phases, surveillance will include assessment for adverse events related to the respective study intervention (i.e. EAD(P) displacement, EAD(P) damage, enteral tract tissue injury) and will continue for three (3) days. Patients who are discharged from the hospital prior to 3 days will be followed up by phone until completion of 3 days following study interventions. All adverse events will be reported to the IRB and medical monitor.

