#### In-vivo Animal Testing

The safety and efficacy of the Alpha (first design iteration) EAD(P) TubeClear® Clearing Stem design was tested in a live porcine model at the Medical University of South Carolina. Use of TubeClear® was performed in a porcine model to simulate pediatric insertion by [name], VMD, a veterinarian, [name], FACG, CNSP, AGAF, FASGE, a gastroenterologist, conducted the standard Intervention and [name], DVM, Ph.D., a board certified pathologist, conducted the pathology evaluations.

1) The efficacy of the EAD(P) Clearing Stem in clearing EAD(P)s with simulated occlusions was evaluated in a porcine model. Patency was restored in an average time of 2.37 minutes (**TP-5017-009**, **TR-5017-009** and **TR-5017-010**).

2) Safety was evaluated in an over-insertion mode (contrary to the Instructions for use). For normal operation, a depth control collar limits the insertion of the Clearing Stem into the EAD; thus prevents the Clearing Stem tip from exiting the EAD. To test safety, the collar was removed, and the Clearing Stem's distal tip was intentionally advanced approximately 2.5cm beyond the distal end of the EAD(P) so that the distal tip contacted and remained in contact with the porcine mucosal intestinal tissue for six (6) minutes while in 'on mode' (**TP-4010-008**, and **TR-4010-008**). No evidence suggested TubeClear® (consistent to instructions for use) produced intestinal trauma beyond that which can be caused by insertion of an EAD(P). In the over-insertion situation (inconsistent to instructions for use), the Clearing Stem caused lesions that were highly localized, but no full puncture was observed.

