## **5.4 Safety Evaluation**

The FDA has deemed TubeClear® to be non-significant risk for use in this study (**Appendix D**). Following successful restoration of EAD(P), a portable abdominal radiograph with contrast agent will be obtained. A radiologist (blinded to the study) will assess the radiographs for adverse events related to the respective Intervention and report results.

Subjects will be monitored for the occurrence of adverse events defined as any untoward or unfavorable occurrence. A description of all events will be recorded in the Study database.

Anticipated adverse events (AE), or “TubeClear® Specified Events” include: EAD displacement, EAD perforation and enteral tract tissue injury.

The relationship of each event to the study protocol will be classified according to severity, expectedness and relatedness by the bedside clinicians and recorded.

Unanticipated Problems (UP) involving risk to Subjects or others will also be tracked. UP includes any incident, experience, or outcome that is unexpected, related or possibly related to Intervention, and suggests that research places Subjects or others at greater risk for harm.

An AE is a reportable Serious Adverse Event (SAE) if it is serious, unexpected and related or possibly related to the Intervention.

**Expedited** reporting timeline for all SAE and unanticipated problems related to the Intervention or from protocol violations:

- a. Principal Investigator or designee will notify their local IRB, medical monitor and AMI **within 24 hours of the event.**

A full narrative report describing the event within 7 calendar days will be submitted to the local IRB, medical monitor and AMI. Such reports will include a detailed description of the SAE/UP, an explanation of the basis for determining that the event represents a SAE/UP, and a description of any corrective actions that are proposed in response to the SAE/UP.

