In Phase IIB, Subject pain will be assessed before and after use of either intervention using established age-appropriate pain scales. Acute changes in physiologic parameters will be measured, including changes in heart rate, blood pressure and respiratory rate. Distress related EAD(P) events which may be manifested by pulling or yanking of the EAD(P) will be monitored in relation to either intervention. Following either intervention, each Subject will receive an abdominal radiograph with contrast. Study procedures carried out in IR may utilize low-dose fluoroscopy as an alternative to the portable abdominal radiograph. Radiographs will be reviewed by a radiologist (blinded to the study) for EAD(P) adverse events (i.e., EAD(P) displacement, EAD(P) damage, enteral tract tissue injury) attributable to either intervention. Incidence of adverse events attributable to the intervention (i.e. EAD displacement, EAD damage, enteral tract tissue injury) following the intervention will be monitored and reported in both groups.

In all phases, surveillance will include daily assessment for adverse events related to the respective study intervention (i.e. subject pain, feeding intolerance, EAD(P) displacement, EAD(P) damage, enteral tract tissue injury) and will continue for three (3) days. Patients who are discharged from the hospital prior to 3 days will be followed up daily by phone until completion of 3 days following study interventions.

1. Intervention time (measured in minutes) is the time interval between commencement of intervention and achievement of EAD(P) patency (if successful).
2. Physiological parameters will be recorded from the Subject's EHR.
3. Distress related EAD(P) events which may be manifested by pulling or yanking of the EAD(P) will be monitored and recorded by Research Personnel or the Subject's nurse.

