#### **6.3.4 Secondary Objective Analysis**

Data from Phase I and Phase IIA will be observational and will not test a hypothesis. Data on 1) pain, using established age-appropriate pain scales, 2) physiologic changes in vital signs, 3) distress related EAD(P) events, and 4) adverse events related to TubeClear® use will be described and reported as counts and percentages.

In Phase IIB, the secondary objectives between TubeClear® intervention and CHOP Standard Treatment include comparison of 1) time to intervention, 2) pain using established age-appropriate pain scales, 3) physiologic changes in vital signs, 4) distress related EAD(P) events, and 5) adverse events related to either group.

1. A log-rank test will be performed to compare intervention time of TubeClear® intervention to the CHOP Standard Treatment.
2. A Wilcoxon rank sum test will be performed to compare differences in subject pain and discomfort between TubeClear® intervention and CHOP Standard Treatment.
3. A t-test will be performed if the distributions are normal (or non-parametric equivalent, if the distributions are not normal) to compare differences in physiologic changes (i.e. vital sign changes) between TubeClear® intervention and CHOP Standard Treatment.
4. A Wilcoxon rank sum test will be performed to compare differences in distress related EAD(P) events (i.e. subject behavior such as pulling/yanking) between TubeClear® intervention and CHOP Standard Treatment.
5. A chi-square analysis (or Fisher's exact test) will be performed to compare the proportions of adverse events (i.e., EAD(P) displacement from the intervention; EAD(P) damage from the intervention; any enteral tract tissue perforation from the intervention) in TubeClear® intervention and CHOP Standard Treatment.

Intention-to-treat analysis will be used to compare the secondary endpoints between the TubeClear® intervention and the CHOP Standard Treatment. Patients will be analyzed according to their randomized allocation. Full reporting of any deviations from random allocation and missing responses will be recorded and assessed in accordance with the CONSORT guidelines. Exploratory-per-protocol analysis will also be reported.

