### **6.3.6 Safety Analysis**

All Subjects entering the Study will be included in the safety analysis. Clinical Patient Assessment Measurements (i.e., pain, feeding tolerance, and usual measures to determine EAD(P) location) will be performed prior to, immediately following, and for up to three (3) days after all Interventions. Clinically significant changes will be addressed and managed by the Subject's medical team, but recorded, reported, and followed by the Study team. Surveillance will include assessment for any adverse event(s) related to the intervention (i.e. EAD(P) displacement, EAD(P) damage, enteral tract tissue injury) and will continue for up to three (3) days following interventions in either group. Patients who are discharged from the hospital prior to three days will be followed up daily by phone for Clinical Assessment Measurements i.e., pain, feeding tolerance and EAD(P) location as assessed by caregiver until post intervention day three.

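### The Phase IIB adverse-event test counts only tissue perforation, although the protocol defines the event as tissue injury; a sentence in 5.4 also conflicts on who is imaged

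*Combined protocol and SAP*

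**What the plan says.** **Event definition.** The list of definitions describes an EAD(P) adverse event as "EAD displacement, EAD damage, enteral tract tissue injury". The Abstract and Sections 2.2, 3.1.2, 3.1.3, 4.2, 4.3, 6.2 and 6.3.6 use the same tissue term. For Phase IIB, Section 6.2 says that the incidence of these events, including "enteral tract tissue injury) following the intervention will be monitored and reported in both groups". Section 5.4 lists "EAD displacement, EAD perforation and enteral tract tissue injury", so there perforation describes the tube and injury describes the tissue.

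Section 6.3.4, item 5, plans a chi-square or Fisher's exact test of adverse-event proportions between the arms. It names displacement and then "EAD(P) damage from the intervention; any enteral tract tissue perforation from the intervention". The list is closed and does not mention non-perforating injury.

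**Analysis sets.** Section 6.3.4 analyses subjects as randomised. Section 6.3.6 says "All Subjects entering the Study will be included in the safety analysis".

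**Imaging.** The Abstract says "Following the use of either standard treatment or TubeClear® intervention, all Subjects will receive an abdominal radiograph with contrast". Sections 2.2, 3.1.2, 4.2 and 6.2 also call for imaging after either intervention without a success condition (4.2 and 6.2 allow fluoroscopy in IR instead). Section 5.4 says "Following successful restoration of EAD(P), a portable abdominal radiograph with contrast agent will be obtained".

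**The concern.** The test in item 5 does not measure the event that its own objective names. Injury and perforation are not interchangeable in this protocol. In the live-animal work in Section 1.3.1, over-insertion contrary to the instructions produced tissue effects short of perforation: "In the over-insertion situation (inconsistent to instructions for use), the Clearing Stem caused lesions that were highly localized, but no full puncture was observed". Lesions of that kind meet the protocol's definition of an adverse event but fall outside the planned comparison.

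The trial report could then carry two adverse-event counts on different definitions, with only the narrower one tested. If the term is settled after the results are known, the choice becomes post hoc. Section 9.5 says the data may be used in a premarket notification, so this matters for the device's safety claim.

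The imaging sentence is a lesser problem. If it were followed, whether a subject has the blinded radiograph would depend on the primary outcome, which the plan expects to differ sharply between arms.

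**Working it through.** **Inputs.** 17 subjects per arm, α = 0.05, and expected success of 95% for TubeClear and 50% for standard treatment (Section 6.4). The test is chi-square or Fisher's exact (Section 6.3.4). Section 6.4 does not state sidedness; two-sided is assumed for the Fisher results.

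**The plan's own figure.** Exact enumeration of two-sided Fisher's test at 0.95 vs 0.50 gives power 0.777 with 16 per arm and 0.813 with 17. The stated 17 per arm is reproduced. It rests on the primary endpoint, so rewording item 5 does not alter it.

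**Effect of the narrower term.** When all k events fall in one of two equal arms of 17, the two-sided Fisher p-value is 2·C(17,k)/C(34,k).

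- k = 4: 2 × 2,380 / 46,376 = 0.103
- k = 5: 2 × 6,188 / 278,256 = 0.0445

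The smallest split against zero that reaches p < 0.05 is therefore 5 vs 0. If those five were non-perforating injuries, the tissue component would be 5 vs 0 with *injury* and 0 vs 0 with *perforation*.

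To show a range, assume a TubeClear injury rate of 10% to 30%, of which 0% to 50% perforate (the documents give neither figure). Expected tissue events in 17 subjects:

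- counted as injury: 17 × 0.10 = 1.7 to 17 × 0.30 = 5.1
- counted as perforation: 0 to 17 × 0.30 × 0.50 = 2.55

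**Effect of imaging only after success, if 5.4 governed.**

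- TubeClear: 17 × 0.95 = 16.15 imaged, about 1 not imaged
- Standard treatment: 17 × 0.50 = 8.5 imaged, 8.5 not imaged

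If no injury is seen among n imaged subjects, the exact one-sided 95% upper limit for the rate is 1 − 0.05^(1/n):

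| Imaged (n) | Upper limit |
|---|---|
| 17 | 16.2% |
| 16 | 17.1% |
| 9 | 28.3% |
| 8 | 31.2% |

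A clean set of films in the control arm would thus rule out much less than one in the TubeClear arm.

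**The case against.** The strongest reply is that this is a wording slip in a secondary safety test with little power. Five of 17 is a 29% injury rate. With no events in control, the chance of a significant Fisher result is about 2% at an assumed true rate of 10%, 24% at 20% and 61% at 30%. The threshold also depends on the test: uncorrected chi-square gives p = 0.033 for 4 vs 0, and the continuity-corrected version gives p = 0.053 for 5 vs 0. Item 5 does not say whether its components are tested separately or together. All of this stands, and 5 vs 0 should be read as an illustration, not a forecast.

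The animal lesions arose with the collar removed, the tip about 2.5 cm beyond the tube and six minutes of contact. Used as instructed, the device showed no evidence of trauma beyond that of placing a tube. Nothing shows that the trial's radiograph would detect such lesions. That limits how often the omitted events might be seen, but it does not make the two terms equivalent.

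Sections 2.2 and 6.2 also list pain and feeding intolerance under adverse-event surveillance. Pain has its own test in 6.3.4, item 2; feeding intolerance has none. Item 5 is therefore the only test of the tube and tissue events, not of everything under surveillance.

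On imaging, the 5.4 sentence does not say *only*, and the sentence after it refers to events of the respective intervention. Section 9.5.3 says tube replacement would involve a radiograph or fluoroscopy, so some failures would have clinical imaging, though not necessarily the blinded contrast study. The three-day follow-up covers everyone. These points make the imaging issue a matter of consistency, not evidence of a selective-imaging design.

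**Conclusion.** The concern holds. Item 5 is the only adverse-event list in the protocol that restricts the tissue component to perforation. Followed as written, it leaves non-perforating injury out of the comparison that the Phase IIB objective calls for. That is a wrong analysis rule, not missing detail.

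The importance is moderate: it should be corrected, but the endpoint is secondary, injuries would still be reported descriptively, and the primary analysis and the 17 per arm are unaffected. The 5 vs 0 illustration assumes Fisher's test on the tissue component alone. The imaging figures apply only if 5.4 is followed, assume the plan's 95% and 50% success rates, and count no other imaging of failures. Because the documents give no injury rate, neither the size nor the direction of any bias can be stated.

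**What to change.** - In Section 6.3.4, item 5, replace the tissue perforation term with enteral tract tissue injury, and list perforation as a subset.
- Reconcile the imaging sentence in Section 5.4 with the Abstract and Sections 2.2, 3.1.2, 4.2 and 6.2 on which subjects are imaged. The same edit could align 5.4's tube perforation with the tube damage used elsewhere.
- Keep the analysis sets already stated: as randomised for the comparison and all subjects for safety.
- Report the number imaged in each arm, split by successful and failed clearance.

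The cost is one phrase in 6.3.4, one sentence in 5.4 and one small table. The tested adverse-event rate may look slightly less favourable. Sample size, α and power do not change.

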### **General overview of Study Treatment Phase – Phase IIB**

- Female patients  $\geq$  10 years of age or those who have experienced the onset of menses must have a documented NEGATIVE pregnancy test (urine or blood).
- Subject will be randomized to either TubeClear® intervention (experimental) or CHOP Standard Treatment (control) group according to randomization sequence.
- Subject's most recent radiograph will be obtained and reviewed by the Investigator to identify EAD(P) characteristics and tube tip location, as well as pre-existing abnormalities, including damage to EAD(P) and/or tissue, if any.
- The Investigator has the option to order a new radiograph prior to the intervention if there is uncertainty about the status of the EAD(P) tube tip location and characteristics.
- The Subject's Nurse will obtain standard baseline measures of Subject pain.
- Subject will receive TubeClear® intervention or CHOP Standard Treatment based on the randomization assignment.
- If randomized to TubeClear®, EAD(P) length will be determined by review of Subject's EHR and/or markings on the EAD(P). The Investigator will place the Operator-set Collar to the same length determined by review of Subject's chart and/or markings on the EAD(P). The TubeClear® Instructions for Use (i.e., Operator's Manual) will be followed by the user to restore patency to the EAD(P).
- If randomized to CHOP Standard Treatment, the CHOP protocol to restore patency to occluded EAD(P) will be followed.
- Data will be gathered or abstracted from the EHR prior to, during the Subject receiving either intervention, and through the follow-up period. This data includes subject name, date of birth, contact information for parent/guardian, age, sex, ethnicity, weight, stature, BMI, location (PICU/PCU/IR), dates of hospitalization (length of stay),

medical record number (MRN), contact serial number (CSN), diagnosis, procedures performed, medications administered, laboratory and radiology results, ventilator parameters (if ventilated), severity of illness, nutrition information, information on EAD and clog, and physical assessments with vital signs (patient temperature, heart rate, respiratory rate, blood pressure and pain level).

- Nursing assessment using the appropriate scale of the Subject's pain prior to and following the respective intervention will be abstracted from the medical record.

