- Intervention in either group is deemed successful if EAD(P) is able to be flushed with 10 ml of air within five (5) minutes following the respective intervention. The intervention is deemed unsuccessful if EAD(P) is unable to be flushed with 10 ml of air within five (5) minutes following the intervention.
- Subject will receive a portable abdominal radiograph with contrast agent following either intervention. The radiologist (blinded to the study) will assess and report the abdominal radiographs post-intervention for adverse events (i.e., EAD(P) displacement, EAD(P) damage, enteral tract tissue injury) attributable to the intervention. Study procedures carried out in IR may utilize low-dose fluoroscopy as an alternative to the portable abdominal radiograph.
- In either group, if the intervention is unable to restore EAD(P) patency, further steps to restore patency will be determined by the clinical team per usual practice.

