#### **4.7    Subject Completion/Withdrawal**

Subjects may withdraw from the Study at any time without any change in their clinical management for any reason that the Subject, parent(s) or guardian(s) provide. They may also be discontinued from the Study at the discretion of the Principal Investigator if any significant Adverse Events (AEs) occur, or if the attending physician requests discontinuing a Subject if there is a perceived interference with a planned procedure. The Principal Investigator or the Study Sponsor may also withdraw Subjects who are not compliant with the Study plan, or to protect the Subject for reasons of safety or for administrative reasons. It will be documented whether or not each Subject completes the clinical Study. If the Principal Investigator becomes aware of any serious, related adverse events after the Subject completes or withdraws from the Study, they will be recorded in the source documents as well as on the Case Report Forms (CRF) with appropriate notification to the IRB.

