##### **4.7.1    Early Termination Study Visit**

Subjects who withdraw from the Study will receive care according to CHOP standard procedures without any change to their clinical care. Adverse events from Study Intervention will be assessed for up to three (3) days following Intervention or until patient discharge (whichever is earlier). Patients who are discharged from the hospital prior to three days will be followed up daily by phone for Clinical Assessment Measurements (i.e., pain, and feeding tolerance) until post Intervention day 3.

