## **6.4 Sample Size and Power**

[figure not shown]
Sample size has been selected such that the power ( $1 - \beta$ ) of primary endpoints is  $1 - \beta \geq 0.8$ , with  $\alpha = 0.05$ .

- The efficacy of TubeClear® is expected to be at least 95% based on previous bench testingxi. The efficacy of CHOP Standard Treatment is expected to be about 50% based on focus group conclusions.xii Sample size results, displayed graphically, are as follows:

---

xi TP-5007-079 and TR-5007-079

xii Conclusions of Clinician Focus Groups, July 2009

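### Phase IIB adverse events are compared by randomized allocation; group the harm table by the first study intervention received (small effect, and only if a child is not treated as allocated).

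*Combined protocol and SAP*

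**What the plan says.** Section 6.3.4 lists adverse events as the fifth Phase IIB secondary comparison, tested by chi-square or Fisher's exact test. The events counted are tube displacement, tube damage and enteral perforation, each attributed to the intervention.

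The same section applies one rule to all the secondary comparisons: "Intention-to-treat analysis will be used to compare the secondary endpoints between the" two groups, with patients kept in their randomized arm. It makes no exception for harms. It adds that "Exploratory-per-protocol analysis will also be reported", without defining that analysis, and asks for deviations from allocation and missing responses to be reported.

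Section 6.3.6 says: "All Subjects entering the Study will be included in the safety analysis". It does not require that an intervention was started, and it gives no grouping rule.

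Section 4.7.1 times the observation from treatment: "Adverse events from Study Intervention will be assessed for up to three (3) days following Intervention". Under section 3.2 the randomization envelope is opened after consent and enrolment, hence before treatment. Section 4.7 allows withdrawal at any time.

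**The concern.** The endpoint is defined by cause, so it belongs to the intervention the child actually had. The grouping is defined by assignment. The two agree only when every child is treated as allocated.

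If a child receives the other intervention, a harm from one method is tabulated under the other. If a child is never treated, no event can be attributed to an intervention and the observation window in 4.7.1 never opens, yet the child stays in the denominator. The exploratory per-protocol analysis may not repair this. On its usual meaning, which is an assumption here, it leaves the deviating child out, so neither planned comparison would show the event under the method that caused it.

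The error can run either way. A device-allocated child given standard treatment can charge a standard-treatment harm to the device, while an untreated device-allocated child lowers the device rate. With 17 children per arm and few events expected, readers will look at the counts themselves.

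**Working it through.** **Inputs.** 17 per arm, planning success rates of 95% and 50%, alpha 0.05 and power of at least 0.80 (section 6.4). Sidedness is not stated, so two-sided tests are used. The documents give no adverse-event, non-treatment or crossover rate. All deviation and event counts below are therefore assumptions.

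**The plan's own figure.** The exact power of the two-sided Fisher test at 95% v 50% is 0.777 with 16 per arm and 0.813 with 17. The stated 17 per group reproduces, and it is the denominator used by allocation.

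**Check 1: one device-allocated child is given standard treatment and has a harm from it.** Let k be the total number of standard-treatment harms, this child's included, with no device harms. Arms are device v standard.

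- By allocation: 1/17 v (k−1)/17.
- By intervention received: 0/16 v k/18.
- Child left out (assumed per-protocol): 0/16 v (k−1)/17.

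| k | By allocation | By intervention received | Child left out |
|---|---|---|---|
| 1 | 1/17 v 0/17: +5.9 points, p = 1.00 | 0/16 v 1/18: −5.6, p = 1.00 | 0/16 v 0/17: 0.0, not testable |
| 2 | 1/17 v 1/17: 0.0, p = 1.00 | 0/16 v 2/18: −11.1, p = 0.49 | 0/16 v 1/17: −5.9, p = 1.00 |
| 3 | 1/17 v 2/17: −5.9, p = 1.00 | 0/16 v 3/18: −16.7, p = 0.23 | 0/16 v 2/17: −11.8, p = 0.48 |

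An example of the p-value arithmetic, for 0/16 v 3/18: [C(18,3) + C(16,3)]/C(34,3) = (816 + 560)/5984 = 0.23. With k = 1 the apparent direction of harm reverses, but nothing is near significance.

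**Check 2: u device-allocated children are untreated, with j device events among the treated and 0/17 in the standard arm.** The rate by allocation is j/17, and among treated children j/(17−u). The relative dilution is 1 − (17−u)/17 = u/17, which is 5.9% for u = 1 and 11.8% for u = 2.

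| j | All 17 kept | One untreated removed | Two untreated removed |
|---|---|---|---|
| 1 | 5.9%, p = 1.00 | 1/16 = 6.3%, p = 0.48 | 1/15 = 6.7%, p = 0.47 |
| 2 | 11.8%, p = 0.48 | 2/16 = 12.5%, p = 0.23 | 2/15 = 13.3%, p = 0.21 |
| 3 | 17.6%, p = 0.23 | 3/16 = 18.8%, p = 0.10 | 3/15 = 20.0%, p = 0.09 |

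No grouping reaches p < 0.05 in either check.

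**Check 3: no deviations.** Allocation and intervention received coincide, both denominators are 17, and the tables are identical.

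**The case against.** The strongest reply is that a misplaced event could hardly stay hidden. Section 5.4 has each event classified for relatedness, section 7.1 has TubeClear related events reported, and 6.3.4 has deviations reported. With 34 enrolments in Phase IIB, a line listing would settle any single case. This stands, and it limits the point to the layout of the comparative table. Those provisions do not tell the analyst which column or denominator to use.

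Deviations may also be rare. Each intervention is a single procedure with no ongoing adherence (7.1.4), and no crossover is planned. Section 4.7 allows discontinuation "if the attending physician requests discontinuing a Subject if there is a perceived interference with a planned procedure", but that takes a child off the study. It does not move the child to the other intervention, and it is not specific to the time before treatment. This stands too: the documents show that deviations are possible, not that they are likely.

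The untreated child's place in the comparative denominator is partly inferred. It follows from analysis by allocation, but 6.3.6 describes no comparative test, and such a child's outcome might instead be handled as a missing response. The wording should settle this.

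A reader might also infer a built-in route away from the device, because the Phase IIB overview in 4.2 places radiograph review for tube characteristics, "as well as pre-existing abnormalities, including damage to EAD(P) and/or tissue, if any", after randomization. The documents do not support that. Table 1 lists the pre-intervention review before randomization, and nothing says that its findings change the treatment given.

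**Conclusion.** The point holds as a small, conditional improvement. Section 6.3.4 states a rule that groups intervention-caused harms by assignment. If a child is not treated as allocated, the table can show one event under the wrong method or shrink an arm's rate by u/17. The size depends wholly on assumed deviation counts. It is zero if there are none, and it changes no test conclusion with one to three events. It does not threaten the trial's conclusions.

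Three stronger readings are tempting and should not be drawn.

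- *A hidden significant harm.* If a control child received the device and had an event, with five device events in all, p would be 0.34 by allocation (4/17 v 1/17) and 0.046 by intervention received (5/18 v 0/16). Nothing in the documents leads a control child to the device. One given it after standard treatment failed would still count as standard under a first-intervention rule.
- *A shift at four events.* With one untreated child removed, four device events against none move p from 0.103 to 0.044. This happens only because the two-sided Fisher rule drops the opposite tail when the arms are unequal. Section 8.1 anticipates no adverse events.
- *Later rescue steps as a reason to regroup.* After failure, "further steps to restore patency will be determined by the clinical team per usual practice". Section 6.4 states: "The efficacy of CHOP Standard Treatment is expected to be about 50% based on focus group conclusions". So 17 × 0.50 = 8.5 standard-arm and 17 × 0.05 = 0.85 device-arm children would be expected to go on to such steps. A child first treated as allocated is in the same group under either rule, so this does not favour one grouping over the other.

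**What to change.** Amend item 5 of section 6.3.4, and section 6.3.6, so that:

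- the Phase IIB adverse-event comparison uses enrolments in which a study intervention was started, grouped by the first study intervention received;
- the intention-to-treat adverse-event table is kept as supportive, and intention-to-treat is unchanged for efficacy;
- randomized but untreated children are listed separately.

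Optionally, flag events that follow a later clearing or replacement step, so that the table makes their timing visible.

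The cost is a few sentences of text. Sample size and the primary analysis are unaffected, and deviations from allocation are already to be recorded. The downside is that the main harm comparison is not strictly randomized if deviations occur. The supportive table covers that.
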